## Subject Assessment of Local Tolerance

Subject assessment of local tolerance using a 4-point scale will be done within 5 minutes and at 1 hour following administration beginning on Day 2 and continuing through Day 7 of Month 1 and Month 9, as recorded in the subject diary.

For each local skin reaction symptom, descriptive statistics (number of subjects, mean, SD, median, interquartile range, minimum and maximum) will be used to summarize the responses on the 4-point scale (0=None, 1=Mild, 2=Moderate,3=Severe) collected during Day 2 to Day 7 at Month 1 and at Month 9:

- by treatment, visit, day, and timepoint.
- maximum severity score by treatment, visit and day
- maximum severity score by treatment, visit and timepoint
- maximum severity score by treatment and visit
- maximum severity score by treatment and day across visits
- maximum severity score by treatment and timepoints

In addition, for each symptom, the number (%) of subjects in each response category (none, mild, moderate, and severe) will be provided by treatment per visit, day, and timepoint in a similar manner as described above for the summary of responses by the 4-point scale. The maximum severity of symptom will be similarly summarized for each response category (none, mild, moderate, and severe):

- by treatment, visit, and day
- by treatment, visit, and timepoint
- by treatment and visit
- by treatment and days across visits
- by treatment and timepoint across visits (and at post dose timepoint).

All injection site local tolerability assessment scores will be presented in a listing.

## 4.5.6 Laboratory Data

Clinical laboratory values will be provided in conventional units and in standard international (SI) units by the central laboratory.

Summaries of laboratory data using descriptive statistics by treatment group and study visit will be presented based on the SI units, including absolute results and changes from baseline. This includes serum chemistry, hematology, coagulation, hormones (including total testosterone, estradiol, SHBG, and PTH), 25-hydroxyvitamin D, 1,25-dihydroxy vitamin D, and urinalysis (for quantitative urinalysis assays). In the event of repeat assessments during a visit time point, the last non-missing value per study day/time will be used in the summary statistics. In the event of duplicate assessments at a visit time point, the worst value per study day/time will be used in the summary statistics. Results from unscheduled visits will not be included in the summaries.

Shift analyses of laboratory data from baseline to the worst post-baseline value and from baseline to Month 12/ET (Visit 8) will be performed by treatment group. Results for serum chemistry,

hematology, coagulation, and urinalysis will be presented by category (above normal limit, within normal limit, below normal limit). For shift tables from baseline to worst post-baseline value, and for baseline to Month 12, percentages will only be calculated based on the number of subjects with valid data for baseline and post-baseline; subjects who are missing either assessment will not be included in the percentage calculation (numerator or denominator). Results from unscheduled visits will be included in the shift analyses, as applicable.

To explore the effect of the COVID-19 pandemic, summaries of all laboratory parameters will also be presented for the following:

- By region (North America and Europe)
- By subject's study status relative to COVID-19 pandemic onset (subjects who completed or withdrew from the study before 01 March 2020, vs subjects who completed or withdrew from the study on or after 01 March 2020)

Any laboratory parameter value that is provided as "< *numeric value*" or "> *numeric value*" will be imputed as the *numeric value* in all summary tables and analyses; but will be shown with the actual result in the listings.

All laboratory data, including repeated values and results from unscheduled visits, will be presented in data listings, with indication of higher or lower than the associated normal range of each laboratory test, where applicable.

## Potentially Clinically Significant Laboratory Values

Criteria for determining values of laboratory tests that are considered Potentially Clinically Significant (PCS) are in Appendix B of this SAP. The number (%) of subjects with at least 1 post-baseline PCS values who did not have PCS values at baseline will be presented for each laboratory parameter. Results from unscheduled visits will be included in identification of subjects with post-baseline PCS values, as applicable. For the calculation of the percentages of subjects, the denominator will be based on the number of subjects who had no PCS values at baseline and had at least one post-baseline assessment for the specific laboratory parameter of interest. The numerator will be based on the number of subjects from the denominator who had at least one PCS value post-baseline for the specific laboratory parameter of subjects with any PCS values will be provided.

## Hypercalcemia

A hypercalcemic event (hypercalcemia) is defined as an elevated serum calcium (albumin-corrected) value  $\geq 0.3$  mg/dL ( $\geq 0.08$  mmol/L) above the upper limit of the normal range (ULN).

Three cutoff levels of serum calcium (albumin-corrected):

- a)  $\geq$  ULN
- b)  $\geq$  ULN+ 0.3 mg/dL (or + 0.08 mmol/L)
- c)  $\geq$  ULN + 1.0 mg/dL (or + 0.25 mmol/L)

The following summaries and analyses will be provided by treatment group for each of the cutoff levels above:

• Number (%) of subjects with at least one occurrence of a serum calcium (albumin-corrected) value above the cutoff level at each visit, timepoint, and overall (entire treatment period):

Study BA058-05-019 SAP

- The corresponding 95% CI based on Wilson's Score method will be provided per treatment group.
- For the number of subjects with at least one occurrence of a serum calcium (albumincorrected) value above the cutoff level during the entire treatment period:
  - The treatment groups will be compared using the chi-square test.
  - The risk reduction between the treatment groups (calculated as Abaloparatide-SC Placebo) will be provided together with the 95% CI based on Newcombe's method.
  - The relative risk reduction between the treatment groups (calculated as (Abaloparatide-SC – Placebo)/Placebo) will be provided together with the 95% CI based on Wald's method.
- Number of occurrences of a serum calcium (albumin-corrected) value above the cutoff level per subject during the entire treatment period
- The ratio of the total number of occurrences of a serum calcium (albumin-corrected) value above the cutoff level to the total number of serum calcium (albumin-corrected) blood samples per subject during the entire treatment period.

Mean ( $\pm$ SE) serum calcium (albumin-adjusted) values will be plotted over study visit by treatment group. All serum calcium (albumin-corrected) results will be included in the plot, which will indicate the results at pre-dose and 4-hours post-dose at each visit.

To evaluate the relationship between age and hypercalcemia, the number (%) of subjects with at least one occurrence of hypercalcemia at each visit and overall (entire treatment period) will be summarized by treatment group and age group (< 65, 65 - < 75, and  $\geq$  75 years).

## Hypercalciuria

The number (%) of subjects with at least one occurrence of hypercalciuria (urine calcium/creatinine ratio > 0.4 mg/mg (> 1.131 mmol/mmol)) at Baseline (Day 1), Month 3, and overall will be summarized by treatment group. A 95% CI for the percentage based on the Wilson's Score method will be calculated for each treatment group at each visit and overall. This analysis will be repeated for subjects with one or more occurrences of urine calcium/creatinine ratio > 0.3 mg/mg (> 0.848 mmol/mmol).

To evaluate the relationship between age and hypercalciuria, the number (%) of subjects with at least one occurrence of hypercalciuria at each visit and overall will be summarized by treatment group and age group (< 65, 65 - < 75, and  $\geq$  75 years).

## **Creatinine and Calcium Excretion and Creatinine Clearance**

The 24-hour urine for calcium:creatinine and creatinine clearance are collected at Day 1 and Month 3. The urine sample values will be adjusted for the time period to derive the urine result that is standardized for a 24-hour period. The 24-hour urine results will be summarized descriptively by treatment group and visit. If the end of the collection time of the 24-hour urine is on the same day as the first dose date or within 24 hours from the time of first dose, then the 24-hour urine sample will be considered as a Day 1 sample and will be treated as the baseline sample. Otherwise, the 24-hour urine data will be considered as a post-Day 1 (i.e, post-baseline) sample.

*Study BA058-05-019 SAP* 

The parameters to be summarized include:

- Urine calcium:creatinine ratio
- 24-hour urine calcium excretion (calcium concentration x 24-hour urine volume)
- 24-hour urine creatinine excretion (creatinine concentration x 24-hour urine volume)
- Creatinine clearance (CCr) calculated in two ways:
  - a) Based on 24-hour urine collection
  - b) Based on serum creatinine, calculated using the Cockcroft-Gault estimate, CCr:  $CCr (mL/min) = [(140 - age) * weight * 1.23] \div SCr$

Where:

- Age in years
- Weight in kilograms
- $\circ$  SCr = Serum creatinine in  $\mu$ mol/L.

The following categories of renal function will be defined:

	Cockcroft-Gault Estimated Serum Creatinine Clearance
Normal	$\geq$ 90 mL/min ( $\geq$ 1.5 mL/s)
Mild	$\geq$ 60 mL/min to < 90 mL/min ( $\geq$ 1.0 mL/s to < 1.5 mL/s)
Moderate	$\geq 30~mL/min$ to $< 60~mL/min$ ( $\geq 0.5~mL/s$ to $< 1.0~mL/s)$
Severe	$\geq 15~mL/min$ to $< 30~mL/min$ ( $\geq 0.25~mL/s$ to $< 0.5~mL/s)$

The number (%) of subjects in each renal function category at each visit and overall (across all visits) will be presented by treatment group. A similar summary table will be presented by treatment group and age group (< 65, 65 - < 75, and  $\geq$  75 years).

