- 9. Serum calcium and albumin will be measured predose from the standard chemistry panel on Month 1 and Month 6, and from a separate blood draw at Day 1, Month 3 and Month 9 and 4 hours post dose at Day 1, Month 1, Month 3, Month 6, and Month 9.
- 10. A 24-hour urine collection will be collected at Day 1 and Month 3 and will be used for urinary calcium and urinary creatinine measurements. Subjects will discard the first void and begin a 24-hour urine collection on the day prior to the clinic visit.
- 11. If the subject reports that a fracture has occurred, remind the subject to bring X-rays and any medical reports of the fracture to the next clinic visit. Documentation must be obtained on all new fractures that occur during the study. This documentation should be maintained in the source documents.
- 12. Each DXA for a given subject should be performed on the same machine, and if available, preferably by the same technician. For screening purposes, DXA scans of the lumbar spine, total hip, and femoral neck taken up to 35 days prior to the beginning of the Screening Period, with a study-approved scanner, may be used to determine study eligibility.
- 13. The first wrist DXA will be performed prior to study drug administration on Day 1 and should be performed on the same machine, and if available, preferably by the same technician.
- 14. QCT performed in a subset of subjects at selected study sites.
- 15. Samples will be drawn prior to treatment on Day 1, Months 1, 3, 6, 9, and 12, and the Follow-up Visit scheduled at 1 month after the last dose of study medication.
- 16. The subject will maintain a diary of their assessment of local tolerance beginning on Day 2 and continuing through Day 7 in Month 1, and beginning on Day 2 and continuing through Day 7 in Month 9.
- 17. The subject medication diary will be reviewed by study personnel at each study visit to ensure subject compliance.
- 18. AEs and SAEs will be recorded on the case report forms starting from the time of subject entry into the Screening Period (Visit 1) of the study (signed informed consent) until 30 days after the last dose of study medication. All AEs will be followed until resolution or stabilization. Any SAEs that occur at any time after completion of the study, which are considered by the Investigator to be related to study treatment, must be reported to the Sponsor or its designee.

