6.2.6. Pretreatment Period (Visit 2)

Subjects who are eligible for the study on the basis of screening evaluations will enter the Pretreatment Period of the study and will be provided the calcium and vitamin D supplements required until the next study visit. All subjects will be required to commence calcium 500–1000 mg/day and vitamin D supplements 400–800 IU/day (or doses determined by the Investigator and agreed by the Sponsor Medical Monitor, according to the subject's need). Subjects will also undergo training for medication self-administration during this period; AEs will be recorded, and the following procedures will be performed:

- Symptom-directed physical exam, including assessment for potential vertebral fracture
- Verification of study entry criteria
- Height
- Orthostatic blood pressure and vital signs
- Clinical assessment of new fractures
- Instruct subject on procedures and provide with supplies for collecting a 24-hour urine sample (the sample is to be collected on the day prior to Day 1)
- Injection training for subjects

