8.4. Description of Statistical Methods

8.4.1. General Approach

Analyses will be presented by treatment group (abaloparatide-SC and placebo) and overall, when appropriate. Baseline is defined as the last value obtained prior to the first dose of study medication.

For categorical data, summary tabulations of the number and percentage of subjects within each category of the parameter will be presented. For continuous data, the number of subjects, mean, median, standard deviation (SD), minimum, interquartile range (Q1 and Q3), and maximum will be presented.

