## 3.4 **Baseline Definitions**

The baseline value is defined as the last non-missing value obtained prior to the first dose of study medication, including the screening value, if necessary. If a randomized subject is not treated, the baseline value is defined as the last non-missing assessment.

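### SAP 4.5.6 labels a 24-hour urine finished on an earlier date and more than 24 hours before the first dose as post-baseline, against the plan's own baseline definition (minor)

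*SAP*

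**What the plan says.** SAP 4.5.6, under creatinine and calcium excretion and creatinine clearance, sorts each 24-hour urine by when its collection ended. If that was "on the same day as the first dose date or within 24 hours from the time of first dose", the sample "will be considered as a Day 1 sample and will be treated as the baseline sample". The next sentence covers all remaining samples: "Otherwise, the 24-hour urine data will be considered as a post-Day 1 (i.e, post-baseline) sample".

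The general definition in SAP 3.4 is different: "The baseline value is defined as the last non-missing value obtained prior to the first dose of study medication, including the screening value, if necessary". Protocol 8.4.1 agrees with it: "Baseline is defined as the last value obtained prior to the first dose of study medication". Neither sets a 24-hour limit. SAP Section 5, which lists the changes from the protocol-specified analyses, does not mention the urine rule.

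On the schedule, a footnote to Protocol Table 3 says: "A 24-hour urine collection will be collected at Day 1 and Month 3". Protocol 6.2.6 says of the first one that "the sample is to be collected on the day prior to Day 1", and Protocol 6.2.8 has it begin on the day before the Day 1 visit. Protocol 6.2.7 instead ties the first collection to the day before Visit 1, which Table 3 labels Screening.

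**The concern.** The second sentence of the rule is a catch-all. It takes every sample that fails the first test, whether it failed by being too late or too early. A urine completed before any exposure to study drug cannot be post-baseline in any useful sense, yet the text puts it there.

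No other collection can replace it, since only two are scheduled and the second is at Month 3. An affected man has no baseline value for the urine calcium:creatinine ratio, 24-hour calcium excretion, 24-hour creatinine excretion, or creatinine clearance from the urine collection. The Cockcroft-Gault clearance uses serum creatinine and is not involved. The by-visit urine summaries in SAP 4.5.6 and the Baseline (Day 1) row of the hypercalciuria table would omit his untreated value. The rule does not say which later row, if any, it would enter.

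Three instructions can be applied to the same sample: the urine rule, the general baseline definition in SAP 3.4, and the nominal-visit convention in SAP 3.12. Programmers following different ones would produce different tables.

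**Working it through.** The plan states no figure on this point, so there is nothing to reproduce. The check applies the rule to a range of collection end times and compares the result with SAP 3.4.

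**Inputs**
- Baseline test: collection ends on the first-dose date, or within 24 hours of the first-dose time (SAP 4.5.6).
- All other samples: post-baseline (SAP 4.5.6).
- Comparator: last value before the first dose (SAP 3.4, Protocol 8.4.1).
- First dose at 09:00. This is an assumption and affects only the same-date test.
- The SAP does not say whether the 24 hours run in both directions or only after the dose, so both readings are shown.

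| Collection ended | SAP 4.5.6, 24 h either way | SAP 4.5.6, 24 h after only | SAP 3.4 |
|---|---|---|---|
| 60 days before | post-baseline | post-baseline | baseline-eligible |
| 96 h before | post-baseline | post-baseline | baseline-eligible |
| 49 h before | post-baseline | post-baseline | baseline-eligible |
| 25 h before | post-baseline | post-baseline | baseline-eligible |
| 24.5 h before | post-baseline | post-baseline | baseline-eligible |
| 24 h before | baseline | post-baseline | baseline-eligible |
| 10 h before (23:00 the previous evening) | baseline | post-baseline | baseline-eligible |
| 2 h before (07:00 the same day) | baseline | baseline | baseline-eligible |
| 2 h after | baseline | baseline | not pre-dose |
| 24 h after | baseline | baseline | not pre-dose |
| 25 h after | post-baseline | post-baseline | not pre-dose |
| 89 days after | post-baseline | post-baseline | not pre-dose |

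**What the table shows**
1. Under either reading, urine finished on an earlier date and more than 24 hours before the dose is labelled post-baseline, while SAP 3.4 makes it eligible as baseline.
2. Under the after-only reading the problem is wider. Any collection that ended before midnight on the eve of dosing is labelled post-baseline.
3. The rule also departs from SAP 3.4 the other way. Urine finished up to 24 hours after the first dose is accepted as baseline.
4. A collection begun the day before the visit and ended on Day 1 before the dose is baseline under every reading.

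**Who is affected.** The collection is tied to the visit and the first dose is given at that visit. Moving Day 1 within its ±4-day window therefore normally moves the collection with it. Misclassification needs a man who collected early, or a visit postponed after the urine had been collected. The documents give no rate for either.

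**Effect of the correction.** If collections that ended before the dose follow SAP 3.4, the rows at 24.5 h, 25 h, 49 h, 96 h and 60 days before all become baseline-eligible. The rows at 25 h and 89 days after stay post-baseline.

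**The case against.** The strongest reply is that this is a gap in wording that a sensible programmer would close. The sentence speaks of a post-Day 1 sample, and urine finished before Day 1 is not that in ordinary language. SAP 3.4 already supplies the right answer, SAP 3.12 makes the nominal visit the general convention, and all laboratory data are listed as collected. That limits the likely harm. It does not remove the defect: the catch-all is exhaustive, it equates post-Day 1 with post-baseline, and a specific rule normally overrides a general one.

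The reply is also right about consequences. A reader might infer that misfiled untreated urine dilutes the post-baseline data and always pulls the drug-placebo difference in hypercalciuria toward zero. The documents do not support that. The hypercalciuria analysis reports Baseline (Day 1), Month 3 and overall, with a confidence interval for each arm. It plans no pooled post-baseline rate and no treatment comparison. It counts men with at least one occurrence, so an extra sample from a man who also has a Month 3 urine does not enlarge the denominator. If overall combines the Day 1 and Month 3 samples, relabelling one leaves that count unchanged.

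A reader might also infer that the adverse events of special interest are affected because hypercalciuria is among them. Those events are identified from MedDRA terms, so the urine label does not alter the tables. Change from baseline in 24-hour urine is not named in the urine section either; only the general laboratory wording in Protocol 8.4.5 and SAP 4.5.6 could supply it.

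**Conclusion.** The rule is wrong as written, and the matter is minor. Under either reading of the 24-hour window, a collection finished on an earlier date and more than 24 hours before dosing is labelled post-baseline, contrary to SAP 3.4 and Protocol 8.4.1. The affected man has no baseline for the urine-based measures.

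No numerical size can be attached. The documents give neither the frequency of such collections nor any hypercalciuria rates. The frequency is probably low, because a collection made on schedule is classified correctly. That judgement assumes that sites follow Protocol 6.2.6, 6.2.8 and the Table 3 footnote. A site following Protocol 6.2.7 literally would collect before Screening, and the rule would then generally call its first urine post-baseline.

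The effect stays within descriptive safety summaries of 24-hour urine and, possibly, the by-visit hypercalciuria counts. No efficacy analysis is affected.

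**What to change.** Replace the catch-all sentence in SAP 4.5.6. A 24-hour urine whose collection ended before the first dose is eligible as baseline, and the last such sample is used, as in SAP 3.4. Only a collection that ended after the first dose can be post-baseline.

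In the same edit, state whether the 24-hour window runs before the dose, after it, or both. If urine finished up to 24 hours after dosing is still to count as baseline, declare that as an exception to SAP 3.4.

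Separately, reconcile Protocol 6.2.7 with Protocol 6.2.6, Protocol 6.2.8 and the Table 3 footnote on when the first urine is collected. This bears on the fix: a collection made before Screening would become baseline-eligible although it predates the calcium and vitamin D supplements that start in the Pretreatment Period.

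The cost is a sentence or two in the SAP and a consistency correction in the Protocol, with no new data. The small downside is that some baselines will be more than a day old.

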## 4.5.7 Vital Signs and Physical Examination

The actual value, the change from baseline to each visit, the change from baseline to the worst post-baseline value during the treatment period, and the change from baseline to Month 13 (Follow-up visit) will be summarized for vital signs using descriptive statistics by treatment group. If a subject has repeat assessments on the vital signs at a particular scheduled visit/time point, the last non-missing value will be used for the by-visit summary. Unscheduled assessments will be included in the summaries for the worst post-baseline value or PCS, they will not be included in the descriptive by-visit summary tables.

The number (%) of subjects experiencing post-dose orthostatic hypotension will be summarized by treatment group, visit and time point, and across all visits. Orthostatic hypotension will be defined as a decrease in systolic blood pressure (SBP) of  $\geq 20$  mmHg from supine to standing or in diastolic blood pressure (DBP) of  $\geq 10$  mmHg supine to standing. Results from unscheduled visits will be included in the summaries.

The number (%) of subjects experiencing heart rate increase from pre-dose to post-dose and the number of occurrences per subject will be summarized with various threshold values (ranging from >5 bpm to >40 bpm, with threshold values increasing by 5 BPM). The median, minimum and maximum heart rate increase (in BPM) will be provided per threshold value. The number of occurrences per subject will be summarized using the median, minimum and maximum values.

All heart rate data, including repeat and unscheduled assessments, will be included in determining the increase from pre-dose in this summary.

Criteria for determining values of vital sign measurements that are considered PCS are in Appendix C of this SAP. The number (%) of subjects who have at least 1 PCS vital sign values for each vital sign parameter of interest after the first dose of study drug, but had no PCS values at baseline, will be presented by treatment. Results from unscheduled visits will be included in identification of subjects with post-baseline PCS values, as applicable. For the calculation of the percentages of subjects, the denominator will be based on the number of subjects who had no PCS values at baseline and had at least one post-baseline assessment for the specific vital sign parameter of interest.

A listing of subjects with any PCS vital sign values will be provided.

To explore the effect of the COVID-19 pandemic, the above planned summaries will also be presented for the following:

- By region (North America and Europe)
- By subject's study status relative to COVID-19 pandemic onset (subjects who completed or withdrew from the study before 01 March 2020, vs subjects who completed or withdrew from the study on or after 01 March 2020)

To evaluate the relationship between age and orthostatic hypotension, the number (%) of subjects with at least one occurrence of post-dose orthostatic hypotension at each visit, timepoint, and overall (across all visits) will be summarized by treatment group and age group (< 65, 65 - < 75, and  $\geq$  75 years).

To evaluate the relationship between age and heart rate increase, the number (%) of subjects with at least one occurrence of heart rate increase from pre-dose to post-dose will be summarized with various threshold values (ranging from >5 bpm to >40 bpm, with threshold values increasing by 5 bpm) by treatment group and age group (< 65, 65 - < 75, and  $\geq$  75 years). Descriptive statistics for heart rate increase per threshold value and the number of occurrences of heart rate increase per subject per threshold value will be provided.

Physical examination is performed only at screening visit and will be summarized as described in Section 4.2.

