Symptom driven spinal radiologic assessment			At any time							
Clinical assessment of new fractures ¹¹			Х	Х	Х	Х	Х	X	X	
BMD of lumbar spine, total hip, and femoral neck by DXA ¹²		X				X	X		X	
BMD of wrist by DXA ¹³				Х		Х	Х		X	
vBMD of hip by QCT ¹⁴				Х					Х	
Sample for immunogenicity testing ¹⁵				Х	Х	Х	Х	Х	X	Х
Investigator assessment of local tolerance (dermal reactions assessment)				Х	Х	Х	Х	Х		
Subject assessment of local tolerance ¹⁶				Х				X		
Subject diary review ¹⁷				Х	Х	Х	Х	Х	X	
Document AEs and concomitant ¹⁸ medications		At any time, question subjects at every visit								
Drug supply/resupply/accountability				Х	X	Х	Х	Х	X	

- 1. The window for screening activities is 60 days. Due to the ongoing COVID-19 pandemic or other local/widespread emergencies, if there is a delay in the screening process that would result in a subject remaining in screening for greater than 60 days, the Medical Monitor should be contacted. All safety laboratory results must be reported within 30 days prior to randomization.
- 2. A complete physical examination includes a review of the following systems: head/neck/thyroid, eyes/ears/nose/throat, respiratory, cardiovascular, lymph nodes, abdomen, skin, musculoskeletal, and neurological. Breast, anorectal, and genital examinations will be performed when medically indicated. After screening, any clinically significant abnormal findings in physical examinations should be reported as AEs.
- 3. Including alcohol and tobacco use assessment.
- 4. Blood pressure, heart rate, body temperature, and respiration rate are to be recorded predose at each study visit. Only blood pressure, heart rate and respiration rate are to be recorded one-hour post dose at each study visit during the Treatment Period. All blood pressure assessments need to be orthostatic.
- 5. Height is to be measured at each visit in the standing position using a medical stadiometer.
- 6. ECGs are to be performed predose and one-hour postdose during the Treatment Period.
- 7. All routine urinalysis will be performed on a sample freshly voided during the visit and sent to a central lab for microscopy if test is positive for micro-organisms via dipstick.
- 8. Reflex testing of T3 and free T4 will be performed by the central laboratory for any out-of-range TSH result.

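### Blood-pressure-measured post-dose orthostatic hypotension is counted without regard to the same-visit pre-dose reading, which dilutes the comparison between arms

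*SAP*

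**What the plan says.** SAP 4.5.7 plans this summary: "The number (%) of subjects experiencing post-dose orthostatic hypotension will be summarized by treatment group, visit and time point, and across all visits". The definition reads "Orthostatic hypotension will be defined as a decrease in systolic blood pressure (SBP) of" at least 20 mmHg, or a diastolic fall of at least 10 mmHg, from supine to standing. It is applied to one assessment at a time. On unscheduled readings the section adds: "Results from unscheduled visits will be included in the summaries". The same count is repeated by age group as "the number (%) of subjects with at least one occurrence of post-dose orthostatic hypotension at each visit, timepoint, and overall".

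The paired data exist. Protocol Table 3, footnote 4, states "Blood pressure, heart rate, body temperature, and respiration rate are to be recorded predose at each study visit", then "Only blood pressure, heart rate and respiration rate are to be recorded one-hour post dose at each study visit during the Treatment Period", and finally "All blood pressure assessments need to be orthostatic". There are six treatment visits: Day 1 and Months 1, 3, 6, 9 and 12.

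Elsewhere in SAP 4.5.7 an earlier value is used. Heart rate is counted as "The number (%) of subjects experiencing heart rate increase from pre-dose to post-dose", and the counts of potentially clinically significant vital signs leave out men who were already abnormal at baseline. SAP Appendix C, which lists those criteria, has none for orthostatic change.

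**The concern.** A man whose pressure falls on standing before the injection, and falls again one hour after it, is recorded as having post-dose orthostatic hypotension. No planned table separates him from a man whose fall is new after dosing.

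Such men are likely to be in the trial. Eligibility runs to age 85, stable antihypertensive treatment is permitted (Protocol 4.4), and the entry blood pressure limits in Protocol 4.1 are for a seated or supine reading, so a standing fall is not screened out. The pre-dose reading is also a good control: mean half-life in men is 1.07 hours (Protocol Table 1) with once-daily dosing, so it is nearly free of the previous dose.

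At stake is how clearly the measured-pressure table shows an effect of the injection. With 75 placebo men, a background unrelated to the drug weakens the contrast.

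**Working it through.** The plan gives no rate, power or sample size for orthostatic hypotension, so there is no figure to reproduce. Arm sizes are 150 and 75 (Protocol 8.5). All event rates below are assumptions, shown over a range.

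**1. Fully persistent background.** A share b of men always meets the criterion, before and after dosing. The drug causes a fall in q = 5% of the others. The planned count gives active = b + (1 − b)q and placebo = b.

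| b | Active | Placebo | Ratio | Difference (points) |
|---|---|---|---|---|
| 2% | 6.9% | 2% | 3.45 | 4.9 |
| 5% | 9.75% | 5% | 1.95 | 4.75 |
| 10% | 14.5% | 10% | 1.45 | 4.5 |
| 20% | 24.0% | 20% | 1.20 | 4.0 |
| 30% | 33.5% | 30% | 1.12 | 3.5 |

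Among men negative before dosing the rates are 5% and 0%, a difference of 5.0 points at every b. The ratio is diluted heavily and the difference only modestly.

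**2. No persistence.** Take b = 10% independently at every reading and q = 5% per visit, over six visits.

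- Planned count, active: per visit 0.10 + 0.90 × 0.05 = 0.145, so 1 − 0.855^6 = 60.9%. Placebo: 1 − 0.90^6 = 46.9%. Difference 14.1 points, ratio 1.30.
- New falls, active: per visit 0.90 × 0.145 = 0.1305, so 1 − 0.8695^6 = 56.8%. Placebo: 0.90 × 0.10 = 0.09, so 1 − 0.91^6 = 43.2%. Difference 13.6 points, ratio 1.31.

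At one visit the ratio is 14.5/10 = 1.45 whether or not pre-dose-positive men are removed. In this limit the new count gains nothing and gives a slightly smaller difference.

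**3. Between the limits.** A latent-normal simulation used six visits with paired readings and 300,000 men per arm. There were 16 settings: background 2%, 5%, 10% or 20% per reading; same-visit correlation 0.4 (low) or 0.8 (high); drug shift 0.3 or 0.5 SD.

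- In placebo, 11% to 64% of post-dose falls came from men already positive pre-dose at that visit.
- The ratio was closer to 1 under the planned count in all 16 settings, at one visit and across visits.
- The across-visits difference was smaller under the planned count in 13 settings, equal in 1 and slightly larger in 2.
- At a single visit, new falls over all men gave a smaller difference in all 16 settings and no gain in power.

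Across visits, at 10% background and shift 0.3:

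| Correlation | Count | Active | Placebo | Ratio |
|---|---|---|---|---|
| Low | Planned | 53.3% | 38.1% | 1.40 |
| Low | New falls | 48.8% | 33.0% | 1.48 |
| High | Planned | 41.7% | 29.1% | 1.43 |
| High | New falls | 35.3% | 20.4% | 1.73 |

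For the high-correlation rows, SE = sqrt(pA(1 − pA)/150 + pP(1 − pP)/75):

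- Planned: SE = sqrt(0.417 × 0.583/150 + 0.291 × 0.709/75) = 6.6 points; 12.6/6.6 = 1.9.
- New falls: SE = sqrt(0.353 × 0.647/150 + 0.204 × 0.796/75) = 6.1 points; 14.9/6.1 = 2.4.

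Illustrative power at two-sided 5% is 0.45 for the planned count and 0.64 for new falls. Across visits, power for new falls was equal (2% background, low correlation) or higher in the 16 settings.

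**The case against.** The strongest reply is that the placebo column already shows the background. Randomisation balances it in expectation, safety analysis is descriptive (SAP 4.5), and no test is planned on this count. That stands: this is dilution, not bias between arms. It does not remove the dilution, because the across-visits percentages will be compared directly and separate rows cannot link two readings within a man.

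A second reply is that orthostatic hypotension is not treated unusually. The SAP's serum calcium, hypercalciuria and QTcF threshold counts also set no pre-dose condition, and the vital-sign rule refers to study baseline, not to the same visit. This is fair. The case rests on a same-visit control being available and unused, not on a departure from a uniform SAP convention.

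A third reply concerns precision. In the fully persistent model at b = 10%, the SE falls from 4.5 points to 1.9 points. That contrast depends on pre-dose-negative placebo men having no events at all. If 3% of them had new falls (an assumption), the new-count SE would be about 3.1 points against about 4.9 for the planned count. The gain shrinks but remains.

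Finally, replacing the planned count would remove men who are positive before dosing and fall further afterwards. Conditioning on pre-dose status after Day 1 also selects a post-randomisation subset. Both objections are sound, and they argue for adding a count, not substituting one.

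**Conclusion.** The point holds for the blood-pressure-measured tables in SAP 4.5.7. Falls already present before the injection are scored as post-dose events in both arms. The ratio moves toward 1 wherever falls persist within a man, and the across-visits percentage loses sensitivity to that extent. The size cannot be fixed from the documents: it is small at 2% background or with little persistence, and material at 10% to 20% background with high persistence. By-visit tables gain little or nothing in power. This is a minor, inexpensive improvement to a descriptive table.

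Two stronger readings are tempting but unsupported. A reader might infer that the special-interest outcome is compromised. SAP 4.5.3 identifies that outcome from MedDRA terms on reported events, under a treatment-emergent definition that already handles pre-existing events, so those tables are untouched. A reader might also infer that the age table will show a rise from background alone. The documents give no age gradient for orthostatic falls, and that table is split by treatment, so a placebo rise would be visible.

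**What to change.** In SAP 4.5.7, keep the planned count for all men. Add a count of new post-dose orthostatic hypotension: criterion met post-dose and not met pre-dose at the same visit. Put it in the across-visits and age-group tables, and by visit for description.

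- **By-visit denominator:** men with both readings who were negative pre-dose.
- **Across-visits denominator:** all treated men with at least one visit with paired readings, so that it does not depend on pre-dose status after randomisation.
- **Pre-dose rate:** show it by visit and arm.
- **Unscheduled readings:** those without a same-day pre-dose pair stay in the planned count only.

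The cost is SAP wording, a little programming on data already collected and one more table line. Men without paired readings drop out of the new count, but remain in the planned one.
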